### **12) Potential Benefits to Subjects**

Subjects may experience relief of or decrease in their symptoms of nausea, pain, anxiety, and/or insomnia with the use of aromatherapy. They may resultantly use less medications and have fewer associated undesirable side effects from those medications.

The results of this study may contribute to our knowledge about aromatherapy as a non-pharmacologic intervention to relieve or minimize pain, anxiety, nausea, and/or insomnia. Future individuals who have such symptoms may benefit as a result.

### **13) Sharing of Results with Subjects**

Results will be shared with subjects. Any peer reviewed manuscripts that result from the study will be made available to the subjects on request.

### **14) Prior Approvals**

The research team has already obtained approval from the Product Standards

---

## PROTOCOL TITLE: Aromatherapy on Tower 4 (Non-Otolaryngology)

Committee. The team has also communicated with and will continue to coordinate with the manufacturer of the aromatherapy tabs, Beekley Medical, regarding procurement. A letter of support noting the agreement from the manufacturer to supply 100 aromatherapy tabs at no cost is enclosed (Attachment A).

### **15) Provisions to Protect the Privacy Interests of Subjects**

Steps will be taken to protect subjects' privacy interests. Subjects will only interact with approved study personnel who have successfully completed human subjects training. This includes those involved in the study visits, consent, and in any study related procedures. We will do our best to make sure that the personal information in the subject's medical record is kept private. However, no study can guarantee 100% protection of confidential information despite all our measures to protect each subject's privacy. Subjects will be made aware of this during the consent process.

### **16) Compensation for Research-Related Injury**

The research study does not involve more than Minimal Risk. If a subject is injured as a result of being in this study, the University of California will provide necessary medical treatment. Depending on the circumstances, the costs of the treatment may be covered by University or the study sponsor or may be billed to the subject's insurance company just like any other medical costs. The University and the study sponsor do not normally provide any other form of compensation for injury. For more information about compensation, call the IRB administration at [contact] or email at [[contact]](mailto:[contact]).

### **17) Economic Burden to Subjects**

No expenses will be billed to conduct the study, printing costs for study document and analysis are supported by the Center for Nursing Science. No study-related procedures or costs are billed to subjects.

### **18) Drugs or Devices**

No drugs or devices will be used for this study. The aromatherapy tabs will be intended to supplement subjects' medication plan. Per Elequil, the aromatherapy tabs are neither considered a drug or device. See letter from Elequil (Attachment B).

### **19) Review Requirements**

There are no contractual obligations or other considerations that require IRB review of this research, or review at intervals other than those required by the Common Rule or FDA.

## PROTOCOL TITLE: Aromatherapy on Tower 4 (Non-Otolaryngology)

### Assessment Tools

**Anxiety Likert Scale:** This one-item scale consisted of five evenly spaced numbers each anchored to a level of anxiety (0 = not at all anxious, 2 = a little anxious, 3 = moderately anxious, 4 = very anxious, 5 = extremely anxious).

**The Numerical Rating Pain Scale** measures pain experienced right now based on a 11-point Likert scale with choices of 0 = no pain, 5 = Moderate pain, 10 = Worst possible pain. We will be utilizing this 0-10 scale for pain because it is one of the most commonly used pain scales that is used at the bedside.

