### 5) Study Timelines

Participants of the study will ideally wear the aromatherapy tab on their gown for at least 8 hours to assess its effectiveness. After a minimum of 8 hours has elapsed, they will be given a follow up assessment tool to evaluate their symptoms and their experience in using aromatherapy.

- Identification of eligibility
- Consent
- Assessment 1 (Hour 0)  
Awake - complete assessment tool.
- Aromatherapy tab application
- Assessment 2 (Hour 8)  
Sleeping - no assessment/document sleep  
Awake – complete end assessment tool.  
Satisfaction assessment

If patient prefers, they can continue to utilize aromatherapy, otherwise tab is to be removed, and study is complete.

- Assessment 3 (Hour 12-24)
- Aromatherapy tab removal (after the maximum 24 hours worn)
- Additional data collection as noted below (medication use)

Individual subject participation will total up to 8 hours to a maximum of twenty-four hours.

We anticipate that our goal enrollment of one hundred subjects will be accomplished within six months (from first subject enrolled to last subject). Our total estimate for study completion is twelve months.

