### 6) Study Endpoints

**Primary endpoint:** Elequil aromatherapy tab use is effective on

1. Patient-reported pain score
2. Patient-reported anxiety score
3. Patient-reported nausea score

**Secondary endpoints:** Elequil aromatherapy tab use is effective in decreasing the following as measured by the corresponding scales:

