### 7) Procedures Involved

#### Methods:

Staff education will be completed prior to the start of the study. Staff will watch a short instructional video. <https://vimeo.com/276457486>. They will then practice how to open the Elequil tabs. Staff will be educated on how to introduce the study to eligible patients.

Upon admission to Tower 4 - an acute care, remotely monitored telemetry unit at UC Davis Medical Center in Sacramento, CA., the bedside RN will introduce the study to the patient. If they are interested in participating, the patient will be evaluated by a member of the research team on whether they meet the inclusion criteria to participate in the study. If inclusion data is met, the research team member will fully introduce and explain the study to the patient. If the patient is interested in participating in the study, the research team member will consent the patient.

After consent is obtained, a baseline assessment tool will be given to the subject for completion, asking them to rate their pain, anxiety and/or nausea using a Likert scale.

Upon completion of these assessment tools, the subject will be asked to identify their highest priority among the symptoms ranked to which they will then be given the corresponding aromatherapy tab to treat that symptom.

The research team member will then provide the tab that is identified to treat that symptom.

- Lavendar: Promotes relaxation, comfort, and sleep. Assists with decreasing anxiety.
- Lavendar-sandalwood: Promotes relaxation, comfort, and sleep. Assists with aches and restlessness.
- Lavendar-peppermint: Promotes relaxation during pain, calm

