### 10. Data analysis

The collected data will be analyzed by the study team in consultation with [name], CTSC Statistician, and [name], Clinical Nurse Scientist.

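### The anxiety item behind a primary endpoint is called evenly spaced but coded 0, 2, 3, 4, 5, so its lowest step counts double if the codes are analysed as numbers

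*Protocol*

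**What the plan says.** The protocol, section 6 (Study Endpoints), lists three primary endpoints, and the second is "Patient-reported anxiety score". Section 7 (Procedures Involved, Methods) has subjects complete a baseline tool "asking them to rate their pain, anxiety and/or nausea using a Likert scale", and the ratings are repeated at follow-up, so the quantity of interest is a within-person change.

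The scores are defined only under Assessment Tools. There the anxiety item is described as "five evenly spaced numbers each anchored to a level of anxiety", and the values are then given as "0 = not at all anxious, 2 = a little anxious, 3 = moderately anxious, 4 = very anxious, 5 = extremely anxious".

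On analysis, the protocol says only "The collected data will be analyzed by the study team in consultation with" a statistician and a nurse scientist. It does not say whether the score is treated as a number or as ordered categories. That choice may properly sit in a statistical analysis plan and is not criticised here. It matters only because nothing in the protocol offsets the coding error.

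**The concern.** The description and the list disagree within one sentence. Five levels are announced and five are listed, so no level has dropped out; the numbering is wrong. The 0 may be a misprint for 1, giving 1–5, or a 0–4 scale may have been meant. The patient form and the database are not in the document, so it cannot be told which codes subjects and staff will use.

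The neighbouring scales do not have this fault. Pain runs from 0 to 10, and the nausea scale runs from 0 to 5 with every value defined, including 1. Staff will therefore be using a nausea scale with a valid 1 beside an anxiety scale without one. A recorded anxiety score of 1 is a plausible slip, and under the printed list it would have no meaning.

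At stake is a primary endpoint in which one step of the scale carries twice the weight of the others by accident.

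**Working it through.** **1. The stated property.** The printed codes are 0, 2, 3, 4, 5. The count is 5, as stated. The successive differences are 2−0 = 2, 3−2 = 1, 4−3 = 1 and 5−4 = 1. Even spacing is not reproduced. Either 0–4 or 1–5 would give gaps of 1, 1, 1, 1.

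**2. Exact effect on the mean.** Let E be the even code (1–5) and P the printed code. P equals E except at *not at all*, where P = E − 1. Taking change as follow-up minus baseline, so that negative is improvement:

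mean change in P = mean change in E − change in the proportion rating *not at all*.

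A net gain of 1 percentage point in that category therefore makes the mean more negative by 0.01. Net shifts from −20 to +20 points move the mean fall by −0.20 to +0.20. This needs no assumption beyond numeric use of the codes.

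**3. Effect on a paired test.** The documents give no anxiety distribution, so what follows is assumed illustration with n = 100, the planned enrolment ("our goal enrollment of one hundred subjects").

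*Regular improvement.* Suppose every subject above the lowest level has the same chance of dropping one level. The ratio of mean falls, printed to even, is (share above the lowest level + share at *a little*) ÷ (share above the lowest level). For three assumed baseline mixes, lowest level first, in percent:

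| Baseline mix | Ratio of mean falls |
|---|---|
| 10/20/30/25/15 | (0.90 + 0.20)/0.90 = 1.22 |
| 20/30/25/15/10 | (0.80 + 0.30)/0.80 = 1.375 |
| 30/40/20/7/3 | (0.70 + 0.40)/0.70 = 1.57 |

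The printed codes raise the variance by more than they raise the mean. For drop chances of 10% to 70%, t is 4.9% to 12.7% lower. For the middle mix at a 30% chance:

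- Even codes: mean fall 0.80 × 0.30 = 0.24, SD 0.429, t = 0.24/(0.429/10) = 5.59.
- Printed codes: mean fall (0.50 × 1 + 0.30 × 2) × 0.30 = 0.33, SD 0.637, t = 0.33/(0.637/10) = 5.18.

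*Uneven movement.* In each case below 60 subjects do not change.

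| Case | Moves | Even codes | Printed codes |
|---|---|---|---|
| A | 20 *a little* → *not at all*; 20 *moderately* → *very* | mean 0.00 | mean −0.20, SD 0.985, t = −2.03, p = 0.045 |
| B | the reverse of A | mean 0.00 | mean +0.20, SD 0.985, t = +2.03, p = 0.045 |
| C | 30 *very* → *moderately*; 10 *not at all* → *a little* | mean −0.20, SD 0.603, t = −3.32, p = 0.001 | mean −0.10, SD 0.835, t = −1.20, p = 0.23 |

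For A with printed codes, the mean is (−2 × 20 + 1 × 20)/100 = −0.20. For C with printed codes, it is (−1 × 30 + 2 × 10)/100 = −0.10.

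**4. Which analyses are immune.** The sign test uses direction only and is the same under both codings: p = 1.00 in A and B (20 against 20) and p = 0.002 in C (30 against 10). Ordered-category models are also unaffected. The paired Wilcoxon signed-rank test is affected, because it ranks the size of the changes. With the normal approximation and zeros dropped, its p goes from 1.00 to 0.006 in A and from 0.002 to 0.43 in C. Choosing a rank-based paired test does not by itself remove the problem.

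**The case against.** The strongest reply is that this is probably one wrong digit. Changing the 0 to 1 gives a clean 1–5 scale. The item is described in the past tense, which reads like text copied from an existing instrument, and the real form may be correct. Harm then needs three things together: the misprint reaches the form or database, the codes are used as numbers, and no one notices. A statistician is to be consulted, so the last is not assured. This stands as a limit on the consequences. It does not make the text correct, and the form cannot be checked from the protocol.

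The uneven cases A to C are also constructed, and nothing in the document suggests such patterns. Under regular improvement the test statistic moves by only 5% to 13% and the conclusion in the worked case is unchanged. This is fair. The cases show what can happen, not what is likely. The inflated mean fall remains a real reporting distortion even under the regular model.

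Equal spacing is itself a convention for a verbal item, so the evenly coded result is not the true one in any deep sense. The p-values of 0.045 also take an unadjusted 0.05 as the yardstick, which the protocol does not state; divided over three primary endpoints (0.05/3 = 0.0167), A and B would not reach it. Both points stand. The standard applied here is the protocol's own: it says the scale is evenly spaced, and the printed codes are not.

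Finally, the phrase about even spacing could describe the layout on the page. That would soften the contradiction but would not explain the missing 1.

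**Conclusion.** The concern holds. The only scoring definition for a primary endpoint contradicts itself: the spacing stated is even and the spacing printed is 2, 1, 1, 1. The exact consequence of numeric use is that the mean fall changes by 0.01 for each net percentage point entering or leaving the lowest category. Under assumed regular improvement the mean fall is overstated by 22% to 57% and the paired t is 5% to 13% lower. Under assumed uneven movement, a difference can appear, reverse or disappear.

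All of this depends on the printed codes being fielded and analysed as numbers. A sign test, an ordered-category analysis or a form that already uses consecutive codes would be unaffected. The point should be fixed. It is not fatal, because the five printed codes correspond one-to-one to the five anchor words.

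**What to change.** In Assessment Tools, state one consecutive five-level coding for the anxiety item, either 1–5 or 0–4. The two give identical change scores, so the choice does not matter for the endpoint. Check that the patient form and the database carry the same codes.

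If forms with the printed codes have already been used, map each response to its anchor word and recode before analysis. Flag and count any recorded 1, which has no anchor under the printed list. If more than one form version has been in use, keep the version with each record, because a 1 cannot be interpreted without it.

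The cost is one corrected line and a check of the form and database. No further patients or data are needed.

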### **Nausea Scale: 0-5 Nausea Scale**

- Each patient room has a laminated copy of the scale.
- When assessing patients, nurses show the scale to patients who can read; nurses tell patients who can't read about it.
- Nurses read the scale levels and the descriptors. Patients select their rating and tell the nurse.
- Nurses ask patients what would help them with their signs and symptoms. Patients may choose a pharmaceutical or nonpharmaceutical intervention.
- Nurses assess the patient prior to medication administration and within 30 minutes afterwards to assess effectiveness of interventions. They record both ratings in computer-based documentation and on the medication administration record (MAR).
- Nurses record the patient rating prior to nonpharmaceutical interventions and 30 minutes later in the computer-based documentation or progress notes.
- A report is run daily by unit to ensure that signs and symptoms are being assessed and outcomes recorded.

|   | Measure | Definitions   |
|---|----------------|--|
| 0 | None           | No nausea  |
| 1 | Anticipated    | Nausea is anticipated and prophylaxis medications may be given.     |
| 2 | Mild           | Nausea reported. Able to tolerate food or medications by mouth.            |
| 3 | Moderate       | Nausea persisting. Lacks appetite. Able to eat small meals occasionally.   |
| 4 | Great          | Nausea ongoing. No appetite. Unable to tolerate food/medications by mouth. |
| 5 | Severe         | Nausea with dry heaves reported.   |

Halpin, [name], CNS; Huckabay, [name], PNP, FAAN; Kozuki, [name], AOCNP, CNS, NP, OCN; Forsythe, Deborah RN, OCN. Nursing2010: November 2010 - Volume 40 - Issue 11 - p 18-20. doi: 10.1097/01.NURSE.0000389030.33760.7a

### **Attachment A**

PROTOCOL TITLE: Aromatherapy on Tower 4 (Non-Otolaryngology)

**elequil®**  
**aromatabs®**  
aromatherapy designed  
for the clinical setting

Relax. Relieve. Refresh.®  
100% pure essential oils

Dear [name],

Beekley Medical will provide complimentary boxes of Elequil aromatabs for the UCDMC study.

You will be sent the following at no charge:

#370 Lavender-Sandalwood

#371 Orange-Peppermint

#372 Lavender

This is a value of \$321 that is being waived to support your study.

Sincerely,

[name]

Senior Product Manager

[[contact]](mailto:[contact])

[contact] [name]

**Beekley  
Medical®**  
when your diagnosis  
must be right™

[name] [name] [elequil.com](http://elequil.com)

PROTOCOL TITLE: Aromatherapy on Tower 4 (Non-Otolaryngology)

Attachment B

---

**BEEKLEY MEDICAL®**  
*when your diagnosis must be right®*

Thank you for your inquiry.

Elequil aromatabs® is an aromatherapy product that is not intended to treat or prevent disease. Therefore, FDA clearance or approval is not required as it is not a medical device nor pharmaceutical product.

Should you have any questions or need further assistance, please do not hesitate to contact us at [name].

Beekley Corporation [name] [contact] [contact] Web: [www.beekley.com](http://www.beekley.com)

---

Page 1 of 1
